9.2. Setting

9.2.1. Study Sites

A feasibility assessment was conducted, and a total of 22 sites meeting the study criteria were identified: 6 in Germany, 5 in Italy, 5 in Spain, 4 in the UK, and 2 in France. All sites are hospital-based facilities and had access to eligible medical records of patients treated within oncology, hematology, and/or transplantation wards and ICUs. During this feasibility assessment, sites were evaluated on the following parameters, to determine their suitability for participation:

- Number of eligible patients treated with isavuconazole for either invasive aspergillosis or mucormycosis.
- Location of medical records and continuity of data across wards and staff resources, to be able to abstract the required data.
- Frequency and availability of follow-up data.

The total number of sites who participate in the study may differ from the anticipated number (22), depending on a site's interest and the availability of its staff (considering the COVID-19 pandemic), and access to eligible medical records. The sites will be hospital based; thus, the patient population will consist of those who were either hospitalized or attending a hospital at the initiation of isavuconazole therapy. As invasive aspergillosis and mucormycosis are rare fungal infections, we expect that the pool of potential patients across sites will be small. The total number of patients eligible patient records to which the sites have access was estimated to be about 583.

9.2.2. Inclusion Criteria

Patients must meet all of the following inclusion criteria to be eligible for inclusion in the study:

1. Patient must be aged ≥ 18 years at the time of isavuconazole initiation.
2. Patient must have a record of a diagnosis of invasive aspergillosis or mucormycosis in their medical record at the time isavuconazole was initiated (regardless of whether this diagnosis is suspected or confirmed).ⁱ
3. Patient must have received at least one dose of isavuconazole during the eligibility period (October 15, 2015, to June 30, 2019).^j

ⁱ Documented cases of invasive aspergillosis or mucormycosis will be included (providing the patient meets all other study inclusion criteria), regardless of whether the diagnosis is classified as being 'suspected' or confirmed via mycological or radiological assessments (this includes EORTC/MSG classification of "proven," "probable," and "possible" invasive fungal disease). All available sources will be used to confirm diagnosis (including any text in the medical records [eg, discharge diagnosis] and ICD-10 codes, if available). The level of documentation in the medical records is expected to vary by HCP and by site and/or country.

^j The eligibility period end date is subject to change based on timing of medical record abstraction and anticipated number of potentially eligible patients during the proposed eligibility timeframe.

9.2.3. Exclusion Criteria

Patients meeting any of the following criteria will not be included in the study:

1. Patients who did not receive at least one dose of isavuconazole for treatment of invasive aspergillosis or mucormycosis within the eligibility period.

9.3. Data Source and Data Collection Process

The source for all data collected will be patient medical records. Retrospective data will be abstracted from the medical records of patients and entered into an EDC system by trained local site staff. It is estimated that data abstraction will be completed in approximately 7 months from the point at which the first patient is included in the study for Germany, France, Spain, and the UK (estimated to be from August 2020 to March 2021). For Italy, data collection is anticipated to begin at a later date, and data abstraction will be completed in approximately 3 months from the point at which the first patient is enrolled (estimated to be from October 2021 to January 2022).^k

9.3.1. Study Periods

9.3.1.1. Index Event

[figure not shown]
This is defined as the first initiation of isavuconazole treatment for the invasive fungal infection that was diagnosed during the eligibility period.

9.3.1.2. Eligibility Period

The eligibility period, wherein potentially eligible patients are identified for enrollment, will be from October 15, 2015 (date of isavuconazole approval by the EMA in the EU), to June 30, 2019.^l The end date of the eligibility period ensures that the latest date of isavuconazole initiation will occur at least 6 months before the end of December 2019 (after which point the medical records may contain data related to the COVID-19 pandemic, which is not of interest for this study). This will allow a minimum of 6 months of follow-up from the date of isavuconazole initiation unless the patient dies or is lost to follow-up within this timeframe (see [Figure 1](#)).

^k Dates of medical record abstraction are subject to change based on the volume of potentially eligible patients during the timeframe of the current eligibility period, the timing of study start-up, and the effect of the COVID-19 pandemic on the availability of members of ethical review boards, institutional review boards, and availability of site staff.

^l The eligibility period end date is subject to change based on the timing of medical record abstraction and the anticipated number of potentially eligible patients during the proposed eligibility timeframe.

Figure 1. Overview of Study Periods and Examples of Eligible Cases

9.3.1.3. Data Collection (Chart Abstraction) Periods

Patients who initiate isavuconazole treatment (index event) during the eligibility period (October 15, 2015, to June 30, 2019)^m will be identified and screened for inclusion/exclusion criteria for enrollment into the study.

[figure not shown]
The two main study periods for data collection from each patient's medical chart are:

- **Pre-index event period:** Baseline data on demographics and medical history will be collected based on all available information in medical records before the index event.

^m The eligibility period end date is subject to change based on timing of medical record abstraction and anticipated number of potentially eligible patients during the proposed eligibility timeframe.

- **Post-index event period:** The timeframe for follow-up data collection will begin one day post-index treatment initiation and end at the earliest of the following: 6 months after post-index treatment discontinuation, death, or loss to follow-up, or December 31, 2019 (see [Figure 1](#) and [Figure 2](#)). Key timepoints of interest for assessment of clinical response and safety will be at 6 weeks, 12 weeks, and 24 weeks after initiation of index treatment (see [Figure 2](#)).

Figure 2. Data Collection Periods and Timepoints for Each Patient

FU = follow up.

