9.4.4. Safety

Category	Variable	Timepoint
AEs	
Type of event (documented by ICD-9 code, ICD-10 code or record in the medical chart):
 
 • Blood and lymphatic AE: 
 • Neutropenia; • Thrombocytopenia; • Pancytopenia; • Leukopenia; • Anemia; • Other (specify). • Immune system AE: 
 • Hypersensitivity; • Other (specify). • Metabolism and nutrition AE: 
 • Hypokalemia; • Decreased appetite; • Hypomagnesemia; • Hypoglycemia; • Hypoalbuminemia; • Malnutrition; • Other (specify). • Psychiatric AE: 
 • Delirium; • Depression; • Insomnia; • Other (specify); • Nervous system AE: 
 • Headache; • Somnolence; • Convulsion; 	Index date, post-index period

Category	Variable	Timepoint
	
 • Syncope; • Dizziness; • Paresthesia; • Encephalopathy; • Presyncope; • Peripheral neuropathy; • Dysgeusia; • Other (specify). • Ear and labyrinth AE: 
 • Vertigo; • Other (specify). • Cardiac AE: 
 • Atrial fibrillation; • Tachycardia; • Bradycardia; • Palpitations; • Atrial flutter; • Electrocardiogram QT shortened; • Supraventricular tachycardia; • Ventricular extrasystoles; • Supraventricular extrasystoles; • Other (specify). • Vascular AE: 
 • Thrombophlebitis; • Circulatory collapse; • Hypotension; • Other (specify). • Respiratory, thoracic and mediastinal AE: 
 • Dyspnea; • Acute respiratory failure; • Bronchospasm; • Tachypnoea; • Hemoptysis; • Epistaxis; • Other (specify). • Gastrointestinal AE: 
 • Vomiting; • Diarrhea; • Nausea; • Abdominal pain; 	

Category	Variable	Timepoint

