**Figure 1 Overview of Study Periods and Examples of Eligible Cases**

### 4.2 STUDY PERIODS

[figure not shown]
The index event is defined as the first initiation of isavuconazole treatment for the invasive fungal infection. The index event serves as the point at which (1) a patient

PFIZER CONFIDENTIAL

qualifies for study inclusion, (2) patient follow-up begins, and (3) the patient becomes at risk for experiencing study outcomes. Study periods for data extraction and variable assessment are defined relative to the index event (Figure 1).

- **Eligibility period:** The index date must occur within the eligibility period, which is the timeframe wherein potentially eligible patients are identified for enrolment. *The dates comprising the eligibility period will be October 15, 2015 (date of isavuconazole approval by the EMA in the EU), to June 30, 2019. The end date of the eligibility period ensures that the latest date of isavuconazole initiation will occur at least 6 months before the end of December 2019 (after which point the medical records may contain data related to the COVID-19 pandemic, which is not of interest for this study). This definition will allow for a minimum of 6 months of follow-up from the date of isavuconazole initiation unless the patient dies or is lost to follow-up within this timeframe.*
- **Pre-index period:** *Baseline data on demographics and medical history will be collected based on all available information in medical records before the index event.*
- **Post-index period:** *The timeframe for follow-up data collection will begin one day post-index treatment initiation and end at the earliest of the following: 6 months after post-index treatment discontinuation, death, or loss to follow-up (Figure 1 and Figure 2). Key timepoints of interest for assessment of clinical response and safety will be at 6 weeks, 12 weeks, and 24 weeks after initiation of index treatment (Figure 2).*

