Mycological response	
Mycological success will be defined as eradication or presumed eradication of the original causative organism cultured.
 
Mycological failure will be defined as persistence or presumed persistence.
 
When medical record documentation is not clear to the abstractor as to which category should be specified, the investigator should review all available medical record documentation to determine classifications. If the investigator determines there is not enough medical record documentation to make the classification, he or she will indicate that the response is 'unknown.' Since mycological response classification is important to the study, participating sites will be selected for participation in the study based on their reporting whether they have enough medical record documentation to classify the response.
	Post-index period

PFIZER CONFIDENTIAL

CT24-WI-GL03-RF03 1.0 *Non-Interventional Statistical Analysis Plan For Secondary Data Collection*  
 Study 16-Sep-2020  
 Page 12 of 19

Variable	Definition	Timepoint
Adverse events	Documentation of any adverse event in the medical record or as described by the ICD-9 or ICD-10 systems.	Post-index period
Serious adverse event	Documentation of any serious adverse event in the medical record or as described by the ICD-9 or ICD-10 systems.	Post-index period
Treatment patterns	Documentation of any of the following in the medical record: 
 
• Index treatment modification
 
• Index treatment discontinuation
 
• TDM
 
• Switching to a new antifungal therapy after index treatment discontinuation
 
• Use of subsequent antifungal therapy after end of index treatment
 
• Index treatment administered as part of antifungal combination therapy
 
• Other concomitant treatments not including combination antifungal therapy
 
• Index treatment administered in the outpatient setting following initiation in the inpatient setting
 
	Post-index period
Healthcare resource utilization	Documentation of any inpatient stay (including specialty wards, ICU, ER, general medicine ward, or other) or outpatient visit (not associated with a hospitalization) in the medical record.	Post-index period

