### 6.3 ANALYSIS OF CLINICAL OUTCOMES

Each clinical outcome will be analyzed using counts and frequencies at weeks 6, 12, and 24, along with other descriptive information about the clinical outcome itself.

Additionally, time-to-event analyses anchored on the index date of isavuconazole initiation will be performed using the KM method. For each clinical outcome, the time-to-event analyses will result in a KM plot with summary statistics, including survival-time quartiles and KM estimates at weeks 6, 12, and 24 with accompanying 95% CIs. All analyses will be performed for invasive aspergillosis patients, mucormycosis patients, and for the total study population. If subgroup analyses are pursued, Cox regression will be employed to derive HRs and accompanying 95% CIs.

For the death outcome, patients will be categorized as dead, alive, or unknown at each timepoint of interest, and primary cause of death will be tabulated (Appendix 1, Analysis Table 5.1). For KM analyses, a documented death will comprise the event, and patients will be censored at the date when they are last known to be alive (Appendix 1, Analysis Figure 1; Appendix 1, Analysis Table 5.2).

For the clinical response outcome, patients will be categorized as having clinical success, having clinical failure, or unknown response at each timepoint of interest will be tabulated (Appendix 1, Analysis Table 6.1). In addition, rates of reactivation of the same infection and rates of new infection will be documented overall and specific to whether these events occurred during isavuconazole treatment. For KM analyses, clinical response will comprise the event, and patients will be censored at the earliest timepoint of any of the following: loss to follow-up, end of study, or death (Appendix 1, Analysis Figure 2; Appendix 1, Analysis Table 6.2).

For radiological response, patients will be categorized as having a success, not having a response, unknown response, or not applicable (for the first assessment) at the relevant timepoints of interest (Appendix 1, Analysis Table 7.1). Additionally, radiological examination type and bodily location of the examination will be tabulated. For KM analyses, radiological response will comprise the event, and patients will be censored at the earliest timepoint of any of the following: loss to follow-up, end of study, or death (Appendix 1, Analysis Figure 3; Appendix 1, Analysis Table 7.2).

PFIZER CONFIDENTIAL

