#### **6.4 ANALYSIS OF SAFETY OUTCOMES**

Descriptive statistics will be used to tabulate the occurrence of AEs at week 6 (Appendix 1, Analysis Table 9.1), week 12 (Appendix 1, Analysis Table 9.2), and week 24 (Appendix 1, Analysis Table 9.3). These tables will be repeated for SAEs (Appendix 1, Analysis Tables 10.1, 10.2, and 10.3, respectively). Additionally, these tables will summarize the occurrence of any AE, number of AEs, isavuconazole-related AEs, whether action was taken with isavuconazole, and the AE outcome.

KM plots for time to onset of the first AE will be generated (Appendix 1, Analysis Figure 5), and summary KM statistics will be tabulated (Appendix 1, Analysis Table 11). For KM analyses, onset of the first AE will comprise the event, and patients will be censored at the earliest timepoint of any of the following: loss to follow-up, end of study, or death.

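### The any-AE, AE-count and any-SAE rows at weeks 6, 12 and 24 pool events on and off isavuconazole, with no split by exposure

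*Protocol*

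**What the plan says.** Protocol 9.3.1.3 starts follow-up the day after initiation and lets it "end at the earliest of the following: 6 months after post-index treatment discontinuation, death, or loss to follow-up, or December 31, 2019". SAP 4.2 keeps the same tail, "6 months after post-index treatment discontinuation, death, or loss to follow-up (Figure 1 and Figure 2", but does not list the calendar cut-off.

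Protocol 9.4.4 collects "Type of event (documented by ICD-9 code, ICD-10 code or record in the medical chart", with timepoint "Index date, post-index period". SAP Table 1 defines an AE as "Documentation of any adverse event in the medical record or as described by the ICD-9 or ICD-10 systems" and an SAE as "Documentation of any serious adverse event in the medical record or as described by the ICD-9 or ICD-10 systems", both over the post-index period. Neither definition requires the patient to be on drug.

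SAP 6.4 begins "Descriptive statistics will be used to tabulate the occurrence of AEs at week 6" (Table 9.1), continues with weeks 12 and 24 (Tables 9.2 and 9.3) and repeats the set for SAEs (Tables 10.1 to 10.3). The listed contents are any AE, number of AEs, isavuconazole-related AEs, action taken with isavuconazole and outcome.

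SAP 6.3 does plan a split by exposure for another outcome. Reactivation and new infection are reported "overall and specific to whether these events occurred during isavuconazole treatment".

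**The concern.** A patient who stops isavuconazole in week 2 and moves to another antifungal keeps adding events to the isavuconazole AE and SAE tables up to week 24. Nothing in the SAP text lets a reader see which events began on drug.

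This matters because Protocol 9.11 says that the study will show whether safety events common in the clinical trials are also seen in practice. A reader making that comparison by organ group would naturally turn to the any-AE and SAE rows. Those rows depend partly on how long patients stayed on isavuconazole and on what they received next.

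The related-AE row offers only partial help. Relatedness is a chart field with options yes, no and unknown (Protocol 9.4.4), the plan does not say how unknown is handled, and Protocol 9.11 names AEs among the items less likely to be fully documented.

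**Working it through.** **1. Can stopping the drug end AE counting before week 24?**

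- Tail after stopping (Protocol 9.3.1.3): 6 months = 365.25/2, or about 183 days.
- Last timepoint: 24 × 7 = 168 days after initiation.
- Last eligible initiation, 30 June 2019, to the cut-off, 31 December 2019: 184 days. This reproduces the six-month minimum follow-up stated in Protocol 9.3.1.2.

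Both 183 and 184 exceed 168. Even a patient who stops on the first day is counted through week 24 unless death or loss to follow-up comes first. The SAP's missing calendar cut-off makes no difference at these timepoints.

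**2. Off-drug share for one patient.** With T weeks on drug and a window of W weeks, followed throughout, the share is max(0, W − T)/W.

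- T = 4: (6 − 4)/6 = 33%, (12 − 4)/12 = 67%, (24 − 4)/24 = 83%.
- T = 12: 0%, 0% and (24 − 12)/24 = 50%.

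**3. Off-drug share for a cohort.** The documents give no treatment durations, so this step is an assumption: exponential duration with mean m weeks, deaths ignored. The share of person-time off drug is 1 − m(1 − exp(−W/m))/W.

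| Window W | m = 6 weeks | m = 16 weeks |
|---|---|---|
| 6 weeks | 1 − 6(1 − e^−1)/6 = 36.8% | 1 − 16(1 − e^−0.375)/6 = 16.6% |
| 12 weeks | 1 − 6(1 − e^−2)/12 = 56.8% | 1 − 16(1 − e^−0.75)/12 = 29.6% |
| 24 weeks | 1 − 6(1 − e^−4)/24 = 75.5% | 1 − 16(1 − e^−1.5)/24 = 48.2% |

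**4. Effect of deaths.** Assume a constant death hazard, independent of stopping, that matches the 19% mortality at day 42 quoted from SECURE: λ = −ln(0.81)/6 = 0.0351 per week. The week-24 off-drug share of time alive is 1 − [(1 − e^−24(λ+1/m))/(λ + 1/m)] / [(1 − e^−24λ)/λ].

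- m = 6: 1 − 4.92/16.22 = 70%.
- m = 16: 1 − 9.26/16.22 = 43%.

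**5. What a table row would show.** Assume an event type unrelated to any drug, with a 24-week risk of 20%: h = −ln(0.8)/24 = 0.0093 per week. The share of patients with first onset on drug is h/(h + 1/m) × (1 − e^−24(h+1/m)).

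- m = 6: 5.2%.
- m = 16: 10.6%.

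The any-event row would show 20%.

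**6. Are the inputs for a split available?** AE onset, discontinuation and next-antifungal start are all entered (Protocol 9.4.2 and 9.4.4). Protocol 9.10 says, however, that calendar dates will not be stored and that the EDC will calculate durations. Planned analyses already need the intervals from index to first AE (SAP 6.4) and from index to discontinuation and to switching (SAP 6.5). Index to onset for every AE, not only the first, is the one interval that no planned analysis clearly requires.

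**The case against.** The strongest reply is that the primary safety objective is isavuconazole-related events, and SAP 6.4 reports these as their own item. An event caused by a later drug enters that item only if the chart attributes it to isavuconazole. This stands. A reader might infer that the primary safety result itself is contaminated by off-drug events; the documents do not support that.

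Three further points also stand.

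- Timing is not the only link between event and drug. Action taken with isavuconazole, an AE as reason for stopping or modifying treatment, and a related SAE as cause of death are all abstracted. For safety reporting, Protocol 11 says that attribution is not inferred from timing.
- The total row is not wrong in itself. In step 5 of the working, 20% is the correct 24-week risk after initiation. It misleads only if read as a rate on drug.
- The full six-month tail does not reach the tables, which stop at week 24, and the shares are much smaller at week 6.

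The SAP's table shells sit in an embedded spreadsheet (Appendix 1) that could not be read, so a split there cannot be excluded. The SAP text describes none.

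It might also be argued that Protocol 11 limits recording to attributed events. That rule governs reporting to the sponsor's safety group. The CRF relatedness field allows no and unknown, and Protocol 9.9.2.1 describes all AEs and SAEs. This argument does not remove the gap.

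**Conclusion.** The gap holds for the any-AE, AE-count and any-SAE rows of Tables 9.1 to 9.3 and 10.1 to 10.3. Followed as written, the plan counts every documented event up to each timepoint whether or not the patient is still on isavuconazole. This reads the week labels as cumulative from initiation, which the SAP does not spell out.

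The direction does not depend on a model: anyone who stops before a timepoint and remains alive and in follow-up adds off-drug time to that table. The size does. The percentages in the working rest on assumed mean durations of 6 to 16 weeks and are illustrations, not forecasts. Allowing for deaths lowers the week-24 range modestly, to 70% to 43%.

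The related-AE result is not shown to be wrong. Its weakness is that it relies on a chart field that may be unknown or thinly documented, and the other rows offer no exposure-based check on it. For a descriptive study this is a worthwhile, inexpensive improvement to the safety display. The time-to-first-AE curve is outside this point.

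**What to change.** In SAP 6.4, keep the all-events total and the isavuconazole-related row, and add three panels to Tables 9.1 to 9.3 and 10.1 to 10.3:

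- (a) onset from the index date to the last isavuconazole dose plus a lag that the sponsor fixes in advance;
- (b) onset after that window;
- (c) exposure unknown, for events without a usable onset or stop interval.

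Within (a) and (b), flag events that begin after the start of another antifungal. Do not end the window at the switch, because that would move isavuconazole reactions that appear just after a switch into the later panel.

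State in the data specification that the EDC keeps index-to-onset for every AE, index-to-stop and index-to-next-antifungal, since calendar dates will not be in the data set.

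The cost is SAP wording, one derived exposure class, one flag and confirmation of the stored intervals; no new abstraction fields are needed. The downside is longer tables and a lag length that is a reporting convention, which a sensitivity table can vary.
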